### 2.1 Primary Objective

2.1.1 To evaluate the feasibility of the MAP intervention in colorectal cancer survivors, as characterized by enrollment, intervention adherence, and retention rates.

*We hypothesize >50% of eligible patients will enroll and that >70% of participants will complete the intervention and be retained in the study.*

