### 5.1 Primary Outcome (Feasibility)

Enrollment rate will be calculated as the percent of eligible participants approached who agree to participate.

Participation rate will be calculated as the percent of participants who complete the study intervention among those enrolled.

Retention rate will be calculated as the number of participants who complete the study measures among those enrolled.

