## 9.0 Statistical Considerations

### 9.1 Analysis of Primary Objective

**9.1.1** We will use one-sample tests of negative binomial probabilities and binomial proportions to compare rates of feasibility to hypothesized values. Rates will be summarized using point estimates and 95% confidence intervals. In exploratory analyses, we will compare participants' intervention completion and retention by baseline characteristics using chi-square tests and t-tests.

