### 9.3 Power and Sample Size

The target sample size is based on estimating rates of feasibility measures to inform the design of an efficacy trial. If the recruitment rate is below 50% and intervention completion and retention rates are below 70%, a larger study may not be feasible. Assuming a negative binomial distribution and true rate of 50%, the probability that we would have to approach 61 or more people to recruit 24 is <0.05. Therefore, if we approach  $\geq 61$  participants to enroll 24, it is unlikely the true probability is above 50%, and we will conclude the study may not be feasible. Out of the 24 participants, if the true rate of intervention completion and study retention is 70%, we expect 13 or more will participate/be retained, so if 12 or fewer do not participate/are not retained the study may not be feasible; we have 80% power to test that the hypothesis that the rate is 70% compared to the alternative that is 46% or less. The number of participants interviewed will be determined when theoretical saturation is reached. We estimate that we will need 8-12 participants in each group (rural-urban).

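### The Section 9.3 cut-offs flag only rates significantly below 50% and 70%, the completion rule is worded in reverse, and no criterion says when the 2.1.1 hypotheses are met

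*Combined protocol and SAP*

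**What the plan says.** The primary objective (2.1.1) hypothesizes that ">50% of eligible patients will enroll and that >70% of participants will complete the intervention and be retained in the study". Section 5.1 bases enrollment on eligible people approached, and completion and retention on those enrolled.

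Section 9.1.1 gives the analysis: "We will use one-sample tests of negative binomial probabilities and binomial proportions to compare rates of feasibility to hypothesized values". It adds: "Rates will be summarized using point estimates and 95% confidence intervals". It states neither the direction of the tests nor a significance level.

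Section 9.3 makes two kinds of statement about feasibility.

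- A general one: "If the recruitment rate is below 50% and intervention completion and retention rates are below 70%, a larger study may not be feasible".
- Operating cut-offs. For enrollment, with a true rate of 50%, "the probability that we would have to approach 61 or more people to recruit 24 is <0.05"; if that many are approached, "we will conclude the study may not be feasible". For completion and retention, it expects 13 or more of 24 at a true rate of 70%, then attaches the warning to 12 or fewer people who do *not* participate or are *not* retained. Power is given as 80% for 70% against an alternative of 46% or less.

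**The concern.** The general sentence and the cut-offs in Section 9.3 draw the line in different places. The general sentence puts it at the targets; the cut-offs put it well below them, where the data are statistically incompatible with the target. Results in the gap are under 50% or 70% but trigger nothing.

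The cut-offs take the target as the null hypothesis, whereas 2.1.1 hypothesizes rates *above* the target. Failing to reject a rate of 70% with 24 people is weak evidence that the rate exceeds 70%. Neither 9.1 nor 9.3 gives a numerical criterion for calling the 2.1.1 hypotheses met, so a report could present an unflagged result as feasible.

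Two wording faults add to this. The completion rule counts the wrong people. And the general sentence joins the conditions with *and*, so read literally every rate must fail before concern arises.

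At stake is what the primary objective may conclude, and hence how the pilot informs the efficacy trial that Section 9.3 says it serves.

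**Working it through.** **Inputs.** Targets 50% and 70% (2.1.1, 9.3); 24 enrolled (9.3); cut-offs 61 approached and 12 versus 13 of 24 (9.3). Let T be the number approached to enroll 24, and X the number of 24 who complete (or are retained). Approaches and participants are taken as independent.

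**Formulas.** P(T ≥ N) = P(Bin(N−1, p) ≤ 23). P(T ≤ N) = P(Bin(N, p) ≥ 24). X ~ Bin(24, p).

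**Step 1: reproduce the plan's figures.**

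- Enrollment: P(T ≥ 61 | 0.50) = P(Bin(60, 0.50) ≤ 23) = 0.0462. With 60 it is 0.0587, so 61 is the first count below 0.05.
- Completion or retention: P(X ≤ 12 | 0.70) = 0.0314. With 13 it is 0.0742, so 12 is the last count below 0.05, and P(X ≥ 13) = 0.969.
- Power, 70% against 46%: the one-sided 5% normal approximation gives 0.801, matching the stated 80%. The exact power of the 12-or-fewer rule is P(X ≤ 12 | 0.46) = 0.726.

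Both cut-offs are therefore one-sided 5% tests in the lower tail.

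**Step 2: results in the gap.**

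- 24/60 = 40.0% (Clopper-Pearson 95% CI 27.6–53.5%): not flagged.
- 13/24 = 54.2% (95% CI 32.8–74.4%; one-sided P against 70% = 0.074): not flagged under the intended rule.

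**Step 3: chance of no flag.**

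| Rate | True value | P(not flagged) |
|---|---|---|
| Enrollment, P(T ≤ 60) | 40% | 0.549 |
| | 45% | 0.818 |
| Completion or retention, P(X ≥ 13) | 46% | 0.274 |
| | 50% | 0.419 |
| | 55% | 0.615 |
| | 60% | 0.787 |
| | 65% | 0.906 |

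**Step 4: the reversed wording.** Taken literally, the warning applies when non-completers number 12 or fewer, that is, when 12 or more of 24 complete. That flags 24/24 (no non-completers) and 13/24 (11), but not 11/24 (13). It contradicts the expectation of 13 or more in the same sentence, so 12 or fewer *completing or retained* must be meant. Steps 1–3 use that reading.

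**Step 5: where observed rates cross the targets.** 24/47 = 51.1% and 24/48 = 50.0%, so a rate above 50% needs 47 or fewer approached. 17/24 = 70.8% and 16/24 = 66.7%, so a rate above 70% needs 17 or more. The gap is 48–60 approached and 13–16 of 24.

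**Step 6: how often an observed rate above target occurs.**

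- Enrollment, P(T ≤ 47): 0.08 at a true 40%, 0.50 at 50%, 0.92 at 60%.
- Completion or retention, P(X ≥ 17): 0.19 at a true 60%, 0.565 at 70%, 0.91 at 80%.
- All three, each exactly at target: 0.50 × 0.565 × 0.565 = 0.16 if independent; 0.50 × 0.565 = 0.28 if completion and retention coincide.

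For comparison, a one-sided 5% test *supporting* the hypotheses would need at most 37 approached (P = 0.049) and at least 21 of 24 (P = 0.042).

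**The case against.** A reader might infer that the 2.1.1 hypotheses are never assessed, or that the report could not say how the rates compare with them. The documents do not support that. Section 9.1.1 plans tests against the hypothesized values with estimates and intervals, and a reported 40% or 54% would be visibly below target. What is missing is the direction, the significance level and a criterion for support.

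A reader might also infer that poor rates usually go unnoticed. That depends on how poor. At the plan's own alternative of 46% completion, 27% of studies escape. The high figures belong to true rates 5 to 10 points below target, which 24 people cannot separate from target under any rule.

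It is fair to add that this is an estimation pilot with tentative conclusions. If the general sentence refers to observed rates, it already covers 24/60 together with 13/24; the plan does not say whether it means observed or true rates. The *and* is partly answered too, since the enrollment cut-off acts alone. On the literal wording 13/24 is flagged, but so is 24/24, so that reading cannot stand.

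Finally, the 95% intervals at the cut-offs contain the targets: 27.1–51.8% for 24 of 61 (exact negative binomial) and 29.1–70.9% for 12/24. A two-sided 95% interval beside a one-sided 5% rule is ordinary practice and not an error.

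These points narrow the concern. They do not reconcile the two statements in 9.3, supply the missing criterion or repair the reversed sentence.

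**Conclusion.** The concern holds in a limited form. The cut-offs in 9.3 are correctly calculated, but they flag only results significantly below target, while the same section treats rates below target as a warning. Enrollment of 40% to 50% and completion or retention of 54% to 67% fall between the two. A true 40% enrollment rate goes unflagged 55% of the time and a true 60% completion rate 79%.

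Nothing in the plan says when the 2.1.1 hypotheses count as met, and an unflagged result does not establish them. The completion and retention sentence is reversed as written and needs correcting regardless.

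The figures rest on independent binomial outcomes, approaching continued until 24 are enrolled, and the cut-off of 12 or fewer completing or retained.

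**What to change.** In Sections 9.1 and 9.3:

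1. Correct the completion and retention rule so that the warning applies when 12 or fewer of 24 participate, or 12 or fewer are retained.
2. Apply the warning to any one of the three rates (*or* in place of *and*).
3. Report 48–60 approached, or 13–16 of 24, as *below target, not excluded*, and not as feasible. (48 approached is exactly 50%, which does not meet a hypothesis of more than 50%.) Report 47 or fewer approached, or 17 or more of 24, as *observed rate above target* with its confidence interval, not as proof of the hypothesis.
4. State that the 9.1 tests are one-sided at 5%, matching the 9.3 cut-offs. The 95% intervals can stay.

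This takes a few sentences and no extra patients or data. The cost is a less favorable conclusion. With true rates exactly at target, enrollment is reported above target 50% of the time and completion or retention 56%; all three together about 16% (independent) to 28% (completion and retention coinciding). Letting any one rate trigger the warning also raises the chance of a warning when all three are exactly at target, to 1 − 0.954 × 0.969 = 8% if completion and retention coincide, or 1 − 0.954 × 0.969 × 0.969 = 10% if independent.

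### The count cut-off for intervention completion and retention in section 9.3 is worded backwards: read literally, it flags high completion as a sign that the study may not be feasible.

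*Combined protocol and SAP*

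**What the plan says.** Section 2.1.1 sets the primary hypothesis: ">70% of participants will complete the intervention and be retained in the study". Section 5.1 defines both rates by those who complete. Participation is the "percent of participants who complete the study intervention among those enrolled", and retention is the "number of participants who complete the study measures among those enrolled".

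Section 9.3 turns this into decision criteria. It first gives a benchmark on the rate scale: if "intervention completion and retention rates are below 70%, a larger study may not be feasible". It then gives a count rule for 24 participants. At a true rate of 70%, "we expect 13 or more will participate/be retained", and from this it concludes: "if 12 or fewer do not participate/are not retained the study may not be feasible". The sentence ends with a power statement of 80% for the hypothesis that "the rate is 70% compared to the alternative that is 46% or less".

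The parallel rule for enrolment, also in 9.3, raises its flag when recruitment goes badly. If 61 or more people must be approached to enrol 24, "it is unlikely the true probability is above 50%, and we will conclude the study may not be feasible".

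**The concern.** The clause counts people who do not complete or are not retained, and treats a small number of them as the warning sign. That is the wrong way round. Few non-completers means good completion, yet the rule attaches the infeasibility flag to it and attaches no flag to poor completion.

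Completion and retention are two of the three primary feasibility rates, and this is the only count cut-off given for either. The purpose of the sample size is to inform a later efficacy trial, so the threshold should be quotable in a report as it stands. If it is quoted or applied as written, it gives the opposite answer. If it is repaired only once results are known, the team has to explain an after-the-fact change to a prespecified criterion.

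**Working it through.** **Inputs, all from 9.3.** n = 24; hypothesised rate 0.70; alternative 0.46; cut-off 12; stated power 80%. Let X be the number who complete (or are retained), X ~ Bin(24, p). No significance level or sidedness is stated for this test. I assume a one-sided 0.05, because 0.05 is the level 9.3 uses for enrolment.

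**Step 1: reproduce the plan's own figures.**
- Enrolment rule: needing 61 or more approaches means at most 23 enrolments among the first 60. At p = 0.5 this has probability 0.046, below 0.05. For 60 or more approaches it is 0.059. The stated 61 reproduces.
- Completion at 70%: P(X ≥ 13 | 0.70) = 0.969, which agrees with the expectation of 13 or more.
- Power by normal approximation, one-sided 5%: Φ{[(0.70 − 0.46)√24 − 1.645√(0.70 × 0.30)] / √(0.46 × 0.54)} = Φ{(1.176 − 0.754)/0.498} = Φ(0.847) = 0.801. The stated 80% reproduces on this basis. The two-sided version gives 0.711.

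**Step 2: find what the number 12 must be counting.**
- P(X ≤ 12 | 0.70) = 0.031.
- P(X ≤ 13 | 0.70) = 0.074.

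So 12 completers is the largest cut-off that keeps the false-flag probability under 0.05 at a true 70%. Also, 0.031 = 1 − 0.969, so 12 or fewer completers is the complement of the 13 or more in the preceding clause. The intended flag set is X = 0 to 12.

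**Step 3: translate the clause as worded.** Non-completers number 24 − X. The condition 24 − X ≤ 12 is X ≥ 12, so the literal flag set is X = 12 to 24.

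**Step 4: compare the two rules.**

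| True rate | P(flag) as worded, P(X ≥ 12) | P(flag) on completers, P(X ≤ 12) |
|---|---|---|
| 30% | 3.1% | 98.8% |
| 46% | 42.3% | 72.6% |
| 70% | 98.8% | 3.1% |
| 90% | >99.99% | <0.001% |
| 100% | 100% | 0% |

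The literal rule flags more often as completion improves. Every count from 0 to 24 is flagged by at least one rule, and only X = 12 by both, so they agree at 1 of 25 counts.

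**Step 5: two side points that the wording error does not cause.**
- Counts of 13 to 16 (54% to 67%) fall below the 70% benchmark but pass the corrected count rule. At a true 70% this has probability 0.435 − 0.031 = 0.404. It is the usual gap between a benchmark and a test cut-off.
- The exact power of the count rule at 46% is 72.6%, against the approximate 80% stated. Exact power reaches 80% at a true rate of about 43.6%.

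**The case against.** The strongest reply is that this is an evident slip which no careful reader would follow. The words before the clause expect 13 or more to participate, the words after it name a low alternative, and 9.3 has already said that rates below 70% are the worry. The clause sits in the sample-size section of a 24-person, one-arm pilot and says only that the study may not be feasible. The primary analysis in 9.1.1 (tests against hypothesised values, point estimates and 95% confidence intervals) does not use it, and no stopping, enrolment or safety action depends on it. The 98.8% and 3.1% therefore describe a literal reading that the context rules out, not a bias or a loss of power.

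Most of that stands. The intent is recoverable, the analysis is intact, and the probabilities describe the wording and not the team's likely conduct. It does not follow that the text can stay. This is the only count cut-off for two primary rates, no other section restates it, and the 70% benchmark is a different criterion, as the counts from 13 to 16 show.

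Two narrower objections are also fair. The slip may lie in the direction word instead of the negation: 12 or more not participating is also X ≤ 12 when n = 24. Both repairs give the same rule, so the correction is unaffected. And section 5.1 is weak support, because a cut-off on non-completers would not by itself contradict rates defined on completers. The contradiction rests on 9.3 itself and on 2.1.1.

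**Conclusion.** The concern holds. As written, the completion and retention cut-off contradicts the rest of 9.3 and the hypothesis in 2.1.1, and it gives the opposite flag at 24 of the 25 possible counts. At a true rate of 70% the flag probability is 98.8% as worded against 3.1% as evidently intended; at 46% it is 42.3% against 72.6%. These are exact binomial figures with n = 24 and independent participants.

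The number 12 is sound as a count of completers. Calling it the right critical value assumes a one-sided 0.05 level, which 9.3 does not state for this test. The reversal itself does not depend on that assumption.

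This is a wording error in a decision rule. It is not an error in the sample size or the analysis. It should be fixed because it concerns a stated threshold for primary outcomes, but it does not threaten the validity of the estimates.

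**What to change.** In 9.3, remove the negation so that the count refers to completers: *if 12 or fewer of the 24 participate or are retained, the study may not be feasible*. Keep the cut-off at 12; moving it to 13 would raise the false-flag probability at a true 70% from 3.1% to 7.4%.

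The cost is one clause of wording. Sample size, conduct and analysis methods do not change.

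### The 80% power claimed against a 46% completion or retention rate is not what the 12-of-24 cut-off delivers: exact power is 73%, and 80% is reached only at a true rate of 43.6% or lower

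*Combined protocol and SAP*

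**What the plan says.** Section 9.1 (Analysis of Primary Objective) names the method in general terms: "We will use one-sample tests of negative binomial probabilities and binomial proportions to compare rates of feasibility to hypothesized values". It does not say whether the binomial test is exact or approximate.

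Section 9.3 (Power and Sample Size) then gives a rule for the completion and retention rates, taking 70% as the reference rate among 24 participants:

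- The acceptable side: "if the true rate of intervention completion and study retention is 70%, we expect 13 or more will participate/be retained".
- The unfavourable side: "so if 12 or fewer do not participate/are not retained the study may not be feasible".
- The power claim, in the same sentence: "we have 80% power to test that the hypothesis that the rate is 70% compared to the alternative that is 46% or less".

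No significance level or sidedness is given for this test. The only level in Section 9.3 belongs to the recruitment rule: "the probability that we would have to approach 61 or more people to recruit 24 is <0.05".

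**The concern.** A count rule on 24 participants has exact operating characteristics. Once the cut-off is fixed at 12, the power at any true rate follows from the binomial distribution, with no approximation needed. The 80% does not follow from that cut-off at 46%, so the reader is told that the rule performs better than it does.

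This is the only power statement given for 24 participants on completion and retention, two of the three primary feasibility rates (Sections 2.1 and 5.1). The error that is understated is the one that matters when a larger study is planned: treating as feasible an intervention that fewer than half of those enrolled complete.

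**Working it through.** **Inputs**

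- n = 24, all enrolled participants (Sections 5.1 and 9.3).
- Reference rate 70%, alternative 46%, stated power 80% (Section 9.3).
- Cut-off: 12 or fewer completing or retained is unfavourable, 13 or more is acceptable (Section 9.3). The unfavourable clause literally counts those who do *not* participate. Read that way, the rule would flag the study with probability P(non-participants ≤ 12 | 0.30) = 98.8% when the true rate is 70%, which cannot be intended. The 13-or-more clause shows the meaning.
- Significance level: not stated for this test. One-sided 5% is assumed, by analogy with the recruitment rule, where a level is needed.

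**Step 1. Reproduce the plan's 80%.** One-sample z-test, one-sided 5%, no continuity correction:

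Power = Φ( [0.70 − 0.46 − 1.645 × √(0.70 × 0.30/24)] / √(0.46 × 0.54/24) )

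= Φ( [0.24 − 0.1539] / 0.1017 ) = Φ(0.847) = 0.801

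This test gives exactly 80% at a true rate of 46.05%, so the stated pair (80%, 46%) is matched. Its critical count is 24 × (0.70 − 0.1539) = 13.1. It therefore rejects at 13 or fewer, whereas the plan puts 13 on the acceptable side.

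Other versions give different power at 46%:

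| Method | Power at 46% |
|---|---|
| z-test, one-sided 5%, continuity-corrected | 74.0% |
| z-test, two-sided 5% (or one-sided 2.5%) | 71.1% |
| z-test, one-sided 10% | 88.1% |
| Arcsine, one-sided 5% | 77.7% |
| Exact binomial, one-sided 5% (cut-off 12) | 72.6% |
| Exact binomial, two-sided 5% | 72.6% |

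**Step 2. Identify the test behind the cut-off.** With X ~ Binomial(24, p):

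| Cut-off | Error at 70%, P(X ≤ c given 0.70) | Power at 46%, P(X ≤ c given 0.46) |
|---|---|---|
| 11 | 1.2% | 57.7% |
| 12 | 3.1% | 72.6% |
| 13 | 7.4% | 84.3% |

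Twelve is the largest count with error at or below 5%, so it is the exact one-sided 5% critical value. The recruitment rule in the same section is built the same way. Under the negative binomial at 50%, P(61 or more approached) = 0.046 and P(60 or more) = 0.059, so 61 is also the exact 5% cut-off.

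No integer cut-off on 24 gives both an error of at most 5% and 80% power at 46%. Twelve falls short on power, and 13 exceeds 5%.

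**Step 3. Power of the plan's own rule, P(X ≤ 12 | p)**

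| True rate | Power |
|---|---|
| 42% | 84.2% |
| 43% | 81.6% |
| 43.6% | 80.0% |
| 44% | 78.8% |
| 45% | 75.8% |
| 46% | 72.6% |

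The shortfall at 46% is 80 − 72.6 = 7.4 percentage points. The miss probability is 100 − 72.6 = 27.4% against an implied 20%, a ratio of 27.4/20 = 1.37. For context on what the rule can and cannot detect, it still passes a true rate of 50% about 42% of the time and a true rate of 60% about 79% of the time. Those figures follow from 24 participants and the cut-off, not from the misstated power.

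**The case against.** The best defence is that the 80% is a correct result of a common approximation. Section 9.1 does not specify an exact test, and the power clause speaks of testing a hypothesis about the rate without naming the count rule. If the analysis were run as that z-test, it would reject at 13 or fewer, and its exact power at 46% would be 84.3%, above the claim. So the defect can be described as an unspecified method rather than a miscalculation. That description of the cause is fair, but it does not rescue the statement. Section 9.3 attaches the power to a rule that treats 13 as acceptable. The test that rejects at 13 contradicts that rule and has an exact error of 7.4% at 70%.

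A second objection is that no significance level is stated. This limits the claim that no integer cut-off works, which assumes 5%. It does not touch the 72.6%, which needs only the cut-off, the sample size and the alternative.

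A third objection concerns consequence, and much of it stands. Section 9.3 says the sample size is chosen for estimating feasibility rates, Section 9.1 promises confidence intervals, the conclusion is only that a larger study may not be feasible, and Section 9.2 reads the quantitative results alongside qualitative data. The rule is not a binding stop. In terms of the detectable rate, the correction is from 46% to 43.6%, or 2.4 percentage points. This limits the practical harm but does not make the stated power correct.

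**Conclusion.** The concern holds. With the published cut-off, power at a true completion or retention rate of 46% is 72.6%, not 80%, and 80% is reached at 43.6%. As a whole percentage, 43% is the highest rate with at least 80% power. The figure in the plan is a normal-approximation power placed beside an exact-binomial decision rule.

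The 72.6% rests on two things: 24 participants in the denominator, and the reading that 12 or fewer completing or retained is the unfavourable result. It does not depend on a significance level. The finding that no cut-off achieves both properties assumes a one-sided 5% level. The statement should be corrected because it is wrong for two of the three primary feasibility rates, although the effect on the pilot's conduct and conclusions is modest.

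**What to change.** Keep the 24 participants and the cut-off of 12, and replace the power clause in Section 9.3 with text along these lines:

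> Completion and retention will each be assessed with an exact one-sided binomial rule: if 12 or fewer of the 24 enrolled participants complete the intervention (or are retained), a larger study may not be feasible. The type I error at a true rate of 70% is 3.1%. Power is 73% if the true rate is 46%, and at least 80% if the true rate is 43% or less.

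This wording also removes the slip that counts those who do not participate. Section 9.1 should say that the binomial tests are exact and one-sided and give their level, so that the analysis matches the rule.

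The cost is protocol wording only. No participants, visits or analyses are added; the stated power simply becomes less favourable.
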